1.1.3 TAVI development for chronic dialysis patients

To date, TAVI development for chronic dialysis patients in Japan has been initiated mainly by Osaka University Hospital. Osaka University Hospital performed TAVI using the 1st generation SAPIEN and 2nd generation SAPIEN XT in chronic dialysis patients with symptomatic severe AS, who were not eligible for sAVR under advanced medical care, and in 2015 Maeda et al. reported good results in 17 chronic dialysis patients up to 1 year after the procedure.^[21] As of March 2016, the results in 24 chronic dialysis patients up to 1 year after the procedure have been obtained, and the treatment results are compared favorably with sAVR, the standard therapy. Therefore, TAVI could be a safe and effective treatment method in chronic dialysis AS patients who were not indicated for sAVR, and with no radical treatment available.

As described above, the safety and efficacy of TAVI using SAPIEN and SAPIEN XT in chronic dialysis patients in advanced medical care were evident. However, since newly introduced 3rd generation EWJ-003 has a paravalvular regurgitation preventing mechanism, with reduced diameter, it may serve as a safer and more effective treatment to chronic dialysis patients with multiple complications, bleeding tendency, and increased susceptibility to infection. In order to support the safety and efficacy of TAVI in chronic dialysis patients observed in advanced medical care, hypothesis should be tested in a statistically basis, and further by performing a long-term follow-up for 5 years after the procedure, long-term safety and efficacy need to be confirmed.

Based on the above, we planned this clinical trial to evaluate the safety and efficacy of TAVI using EWJ-003 in chronic dialysis patients.

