4.2 Performance Goal

4.2.1 Rationales for the performance goal setting

The PG was established by estimating mortality at 1 year post-procedure from the clinical research results of sAVR in chronic dialysis patients in Japan.

In the dialysis treatment between Japan and Europe and the US, there are some differences in physique of the patients, formulation of dialysis volume and duration of dialysis, patient control, and treatment compliance, and it is generally known that prognosis is better in Japan relative to Europe and the US. According to a large-scale global observation epidemiologic cohort research on medical care process and outcome of patients on maintenance dialysis (Dialysis Outcomes and Practice Patterns Study [DOPPS]), when the relative death risk adjusted for age, gender, race, and 15 concomitant diseases in Japan is assumed to be 1, it was 3.78 in the US, and 2.84 in Europe^[31]. Compared with non-dialysis patients, chronic dialysis patients have poorer prognosis after sAVR; it has been reported that the survival rate at 1 year post-procedure in the US was approximately 60%, at 3 years post-procedure approximately 40%, and at 5 years post-procedure approximately 30%^[9, 13] whereas in Japan good long-term results have been reported; at 1 year post-procedure 75% to 90%, at 3 years post-procedure 40% to 80%, and at 5 years post-procedure 30% to 60%^[14, 17, 32-33]. Therefore, upon estimating the mortality at 1 year post-procedure in chronic

- 40 -

dialysis patients underwent sAVR, the impact of the difference in the medical environment for dialysis between Japan and Europe and the US cannot be ignored, and thus the mortality at 1 year post-procedure was estimated based on the results of Japanese clinical research.

As shown in Table 4-1, there was no difference in the results of sAVR in chronic dialysis patients by type of artificial valve (bioprosthetic or mechanical valve)^[17, 32] for the setting of PG, regardless of bioprosthetic or mechanical, the results of both valves were used.

Table 4-1: Comparison of sAVR results in chronic dialysis patients by type of prosthetic valve

Author (year of publication/country)	Valve position	Implantation valve	Treatment results			Structural valve deterioration	
			30-day mortality	5-year survival rate ^{†3}			
K. Tanaka, et al ^[32] (2009/Japan)	Aortic valve	Bioprosthetic valve (N=22)	1/22 (4.5%) ^{†1}	---	55.7 ± 7.6%	p < 0.001 ^{†4}	0 subjects (FU: 42 ± 31 m)

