9.2 Secondary Endpoints

9.2.1 Secondary safety endpoints

- Composite endpoint: Post-procedure 30 days, 6 months, 1 year, and 2 to 5 years annually
 - Death and stroke
- Single endpoints: Post-procedure 30 days, 6 months, 1 year, and 2 to 5 years annually
 - Death (cardiovascular, non-cardiovascular)
 - MI (periprocedural, spontaneous)
 - Stroke (disabling, non-disabling)
 - Bleeding (life-threatening or disabling, severe, mild)
 - Vascular access site/access-related complications
 - Severe vascular complications
 - Conduction disorder/arrhythmia
 - Conduction disorder requiring new pacemaker implantation
 - Aortic valve re-intervention
 - Coronary obstruction
 - Endocarditis
 - Valve explants
 - Structural valve deterioration
 - Nonstructural valve dysfunction

Table 10-1: Permissible time windows for the tests/observations

Test/observation timing	Baseline ^{a)}	Procedure ^{b)}	Immediately after procedure	Post-procedural follow-up observation		
				Hospital discharge	30 days post-procedure	6 months post-procedure
Reference date (time)	-	Day 0	Up to 72 hours after exiting the operation room	7 days post-procedure or hospital discharge, whichever comes earlier	30 days post-procedure	182 days post-procedure
Permissible time window	Within 60 days pre-procedure	-	-	± 2 days	-7 days/+14 days	± 30 days

^{a)} The 12-lead ECG should be performed within 48 hours prior to entering the operation room, clinical laboratory tests within 14 days prior to the procedure, and coronary angiography and aortofemoral blood vessel evaluation (CT, MRI, or X-ray) within 90 days pre-procedure (see Section 10.2.1 "Baseline"). For the continued access registry, except cases that may be clinically valid, coronary angiography should be performed within 1 year prior to the study procedure.

^{b)} Cardiac catheter test at procedure should be performed immediately before and after the procedure.

Table 10-2: Permissible time windows for the tests/observations

Test/observation timing	Post-procedural follow-up observation				
	1 year post-procedure	2 years post-procedure	3 years post-procedure	4 years post-procedure	5 years post-procedure
Reference date	365 days post-procedure	730 days post-procedure	1095 days post-procedure	1460 days post-procedure	1825 days post-procedure
Permissible time window	± 30 days	± 45 days	± 45 days	± 45 days	± 45 days

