15.1.1.2 As-treated analysis set

A subject population consisting of subjects who were enrolled in this clinical trial and implantation of the study device was initiated is defined as as-treated (AT) analysis set. The time when invasion such as incision was made on the access site is regarded as the start of the study procedure. The primary endpoint and secondary safety and efficacy endpoints will be analyzed in the AT analysis set.

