15.1.2 Statistical analysis plan and statistical method

Mortality at 1 year post-procedure, the primary endpoint, will be analyzed in the AT analysis set to verify the non-inferiority of EWJ-003 therapy to the standard therapy. The non-inferiority test will be performed

- 104 -

made and reasons for the changes, and the Statistical Analysis Plan should be revised.

All deviations from the Statistical Analysis Plan should be described in the Study Report.

- 106 -

using one-sided Fisher's exact test, and at one-sided significant level of 0.05 if the 95% CI upper limit for the mortality at 1 year post-procedure is lower than the PG (45%), non-inferiority of EWJ-003 therapy to the standard therapy would be verified.

No statistical tests will be conducted for the secondary endpoints, but evaluate by descriptive statistics. The secondary valve performance endpoints based on the echocardiographic evaluation will be analyzed in the VI analysis set, and other secondary endpoints. Other data including subject background and baseline characteristics, and procedure information, etc. will be summarized by descriptive statistics.

All statistical analyses will be performed for, in addition to the entire analysis sets, each approach of TF, TA, and TAO. For continuous variables, the number of measurements, mean, standard deviation, median, quartile, minimum, maximum, and 95% CI of the mean will be calculated. On the other hand, for categorical variables, the number of samples (n), percentage (%), and for binary variables 95% CI will be calculated. For the primary endpoint and secondary safety and efficacy endpoints, the cumulative incidence will be calculated by Kaplan-Meier estimates as needed.

The detailed statistical analysis plan and statistical method are included in the Statistical Analysis Plan.

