	
 First degree atrioventricular (A-V) block Second degree A-V block (Mobitz type I or II) Third degree A-V block Incomplete right bundle branch block Right bundle branch block Defect intraventricular conduction Left bundle branch block Left anterior hemiblock (LAH) Left posterior hemiblock (LPH) Block requiring permanent pacemaker implantation Persistent or transient advanced A-V block 
When advanced A-V block is observed at every test, it is regarded as persistent.
 
 New permanent pacemaker implantation 
The indications of permanent pacemaker implantation and the number of days after the procedure should be accurately recorded.
 
 Newly found atrial fibrillation/flutter Newly found arrhythmia with hemodynamic instability or requiring treatments 	
Switching to surgery	Refers to cases with switching to open heart surgery by sternotomy due to a procedure-related complication during the study procedure.	VARC-2
Coronary obstruction	During the study procedure or post-procedure newly found prosthetic valve, native cusp, lump lime, or partial or total occlusion at the coronary ostium associated with dissociation in the angiogram or echocardiography findings.	VARC-2
Death	
Death is classified into cardiovascular death or non-cardiovascular death by the cause of death.
 
 Cardiovascular death 
 When applicable to the followings, it is regarded as cardiovascular death: 
 Death directly associated with the heart (e.g.: myocardial infarction, cardiac tamponade, worsened heart failure) Death associated with blood vessels other than the coronary artery (e.g.: neurological event, pulmonary embolism, aortic aneurysm rupture, dissecting aneurysm, and other vascular disease) All study procedure-related deaths, including deaths related to procedural complication and treatments for the procedural complication. All deaths related to the investigational valve, including deaths from structural valve deterioration, non-structural dysfunction, and other valve-related AEs. Sudden death and unwitnessed death Death with unknown cause Non-cardiovascular death 
 It is apparent that the major cause of death is a disease other than the above (e.g.: trauma, cancer, suicide) 	VARC-2

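### Kaplan-Meier is the only cumulative-incidence estimator named for endpoints that death can preclude; with deaths censored it overstates late valve events and the two cause-of-death rates

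*Combined protocol and SAP*

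**What the plan says.** Section 15.1.2 of the combined protocol and SAP gives one rule for all endpoints together: "For the primary endpoint and secondary safety and efficacy endpoints, the cumulative incidence will be calculated by Kaplan-Meier estimates as needed". The same section also plans crude summaries without that condition: "On the other hand, for categorical variables, the number of samples (n), percentage (%), and for binary variables 95% CI will be calculated". Secondary endpoints are descriptive, with no tests. Section 15.1.1.2 fixes the population: "The primary endpoint and secondary safety and efficacy endpoints will be analyzed in the AT analysis set".

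Section 9.2.1 sets the horizon: "Single endpoints: Post-procedure 30 days, 6 months, 1 year, and 2 to 5 years annually". The list there includes stroke, endocarditis, valve explant, re-intervention, structural valve deterioration, and death split into cardiovascular and non-cardiovascular. On that split, Section 30 says: "Death is classified into cardiovascular death or non-cardiovascular death by the cause of death". Sudden, unwitnessed and unknown-cause deaths go to the cardiovascular class, so every death falls in exactly one of the two.

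Section 1.1.3 makes the late data a purpose of the trial: "further by performing a long-term follow-up for 5 years after the procedure, long-term safety and efficacy need to be confirmed".

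Section 14.1 lists death as a reason for leaving the trial but does not say whether such a subject is censored or has had a competing event. Section 15.1.2 refers to a separate, detailed Statistical Analysis Plan, whose text was not available for this review.

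**The concern.** Kaplan-Meier treats a censored subject as still able to have the event later. A subject who has died cannot have a stroke or a deteriorated valve, and a subject who died of one cause cannot die of the other. If these deaths are censored, 1-KM estimates the risk in a hypothetical population in which nobody dies of anything else. It does not estimate the share of treated patients who have the event.

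The sentence in Section 15.1.2 does not separate endpoints where the two agree (all-cause death, death or stroke) from those where they differ. Competing mortality is heavy here: Section 4.3 plans for 20% mortality in the first year alone.

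Two consequences follow if 1-KM is used throughout. Late valve-event rates in the 5-year report are too high. The cardiovascular and non-cardiovascular figures add to more than the all-cause figure in the same report. The second needs no assumed event rate: it arises as soon as both kinds of death have occurred.

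**Working it through.** **The plan's own figures.** The plan gives no figure for this point. Its stated power reproduces: success with at most 6 deaths in 24 has exact alpha 0.0364 under 45% mortality and power 0.8111 under 20%, against the stated 81.1%. It does not depend on the estimator questioned here.

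**Inputs**
- From the protocol: 5-year survival of 60% and 30%, the ends of the published range after surgical valve replacement in Japanese dialysis patients (Section 4.2.1). It is used as a range, not as a forecast for these subjects.
- From the protocol: planned 1-year mortality of 20% (Section 4.3), and a 37.7% cardiovascular share of deaths among dialysis patients in general (Section 1.1.2).
- Assumed, because the documents give no values: constant hazards, a 5-year 1-KM of 5% to 20% for a non-fatal event, and a cardiovascular share of 30% to 70%.

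**Non-fatal events.** Let K be the 5-year 1-KM and S the 5-year survival.
- Hazards: λe = −ln(1−K)/5 and λd = −ln(S)/5.
- 1-KM(t) = 1 − exp(−λe·t).
- True incidence(t) = λe/(λe+λd) × [1 − exp(−(λe+λd)t)].

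Example with K = 10% and S = 60%: λe = 0.02107 and λd = 0.10217. At year 5 the true incidence is 0.02107/0.12324 × (1 − 0.90×0.60) = 7.87%. With S = 30%, λd = 0.24079 and it is 5.87%.

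**Death split.** Let S now be survival to time t and p the cardiovascular share. The two 1-KM values are a = 1 − S^p and b = 1 − S^(1−p). Their sum minus all-cause mortality is a + b − (1 − S) = a×b, which is positive once both causes have occurred. With S = 0.30 and p = 0.5, a = b = 0.4523, so the excess is 20.5 points: 90.5% against 70.0%.

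| Year | Non-fatal: 1-KM minus true (points) | Ratio | Death split: excess over all-cause (points) |
|---|---|---|---|
| 1 | 0.05–0.48 | 1.05–1.12 | 0.2–1.3 |
| 2 | 0.19–1.74 | 1.10–1.26 | 0.8–4.6 |
| 3 | 0.42–3.54 | 1.16–1.40 | 1.7–9.2 |
| 5 | 1.08–8.12 | 1.27–1.71 | 4.3–20.5 |

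Out of 30 subjects, the non-fatal gap is 0.06–0.52 at year 2, 0.13–1.06 at year 3 and 0.32–2.43 at year 5.

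**At the plan's own mortality.** Hold 20% a year constant (an assumption) and take p = 0.377. At year 5 the 1-KM figures are 34.3% + 50.1% = 84.4%, against all-cause mortality of 1 − 0.8^5 = 67.2%.

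**Thirty subjects, complete follow-up, 7 cardiovascular and 11 other deaths.** Crude figures: 23.3% + 36.7% = 60.0%. Over 20,000 random orderings of the deaths, 1-KM averages about 30% + 43%, a mean sum of 72.8% (range 71.3% to 73.5%).

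**Sensitivity**
- Death hazards following 90/80/60% or 75/40/30% survival at years 1, 3 and 5: non-fatal gap 0.2–2.1 points at year 2, 0.4–4.2 at year 3 and 0.95–9.0 at year 5 (ratio 1.23–1.86); death-split excess 0.5–6.8 points at year 2 and 0.9–13.5 at year 3.
- Event hazards that start after year 1 or 2, or rise with time, with 20% yearly mortality and a 5-year 1-KM of 10%: true year-5 incidence 4.5% to 5.3%, a ratio of 1.9 to 2.2.
- Events confined to the first 30 days: a 1-KM of 5% is truly 4.95% to 4.98%.

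**The case against.** The best case against is that the plan does not commit to the error. Kaplan-Meier is conditional, and nothing says deaths are censored. The sentence is plainly generic, since it also covers efficacy endpoints such as NYHA class and length of stay that are not time-to-event rates. The separate Statistical Analysis Plan may already deal with competing events. Crude n and % are planned in any case, and in the 30-subject example they add up exactly.

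The sizes also rest on assumed event rates. Table 4-1 reports no structural deterioration in 22 and 23 bioprosthetic valves. At a 5-year 1-KM of 2%, the same formula gives a year-5 gap of only 0.4 to 0.8 points. Sampling error is larger than the bias for a single rate: the exact 95% interval for 3/30 is 2.1% to 26.5%. Cause of death is adjudicated only to 1 year (Section 13.1), and the cardiovascular share of the summed figures moves only from 37.7% to 40.7% in the 20%-a-year case.

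Much of this stands, and it limits the weight of the point. The error is conditional, its size for non-fatal events is illustrative, and the endpoints are descriptive. It does not remove the point. Crude percentages are free of this bias only with complete follow-up, and incomplete follow-up is when a time-to-event estimate is wanted. The direction does not depend on the assumed rates. The failure of the two death rates to add up would show in the report at any sample size.

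**Conclusion.** The concern holds for the sentence in Section 15.1.2. Used with deaths censored, 1-KM overstates late-accruing non-fatal events: little in percentage points at year 2, more from about year 3. It also gives cause-of-death figures that exceed all-cause mortality, by 4.3 to 20.5 points at year 5. These sizes assume constant hazards, survival in the protocol's published surgical range, and illustrative event rates and cause shares. For truly late events, constant hazards understate the relative bias. In relative terms the year-2 figures are already inflated 1.10 to 1.26 times.

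The primary test, sample size, all-cause death, and death or stroke are unaffected. Events confined to 30 days and the 1-year submission data are barely touched. The error overstates harm and does not favour the device. This is a reporting fault worth correcting, not a threat to the primary conclusion. Confidence is medium, because the separate Statistical Analysis Plan could not be checked.

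**What to change.** Replace the sentence in Section 15.1.2, and align the separate Statistical Analysis Plan, with text to this effect:

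- Where a cumulative incidence is reported, Kaplan-Meier is used for all-cause death and for death or stroke.
- For the other event-type secondary safety endpoints, the Aalen-Johansen estimator is used with death as the competing event. For cardiovascular and non-cardiovascular death, the other cause is the competing event.
- Removal of the study valve is a competing event for later valve-specific endpoints such as structural valve deterioration. For valve explant it is the event itself. (Section 14.1 ends participation at removal, so the rule is needed.)
- An event that is itself fatal (fatal bleeding, fatal stroke, sudden-death infarction, all events under Section 30) counts as the event, not as the competing death.
- Subjects are censored at withdrawal, loss to follow-up, end of follow-up, or exit from the trial without a study valve.

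The Aalen-Johansen figures for the two causes of death add exactly to all-cause mortality, also with withdrawals. The cost is about five sentences and a standard software routine, with no new data. The drawback is slightly more analysis work and less direct comparability with the earlier Kaplan-Meier reports for this device in Section 1.2.2.1. A labelled 1-KM supplement covers the latter.

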15.2 Bailout Treatment Registry Statistical Analysis

In this clinical trial, subjects enrolled in the bailout treatment registry will not be included in the analysis set for the safety and efficacy evaluation of EWJ-003. The bailout treatment registry will be analyzed separately as sub-analysis, which will primarily confirm the safety. In this sub-analysis, no statistical tests will be conducted.

15.3 Statistical Analysis of the Continued Access Registry

Subjects enrolled in the continued access registry will not be included in the analysis set for the safety and efficacy evaluation of EWJ-003. The continued access registry will be analyzed separately as sub-analysis, which will primarily confirm the safety. In this sub-analysis, no statistical tests will be conducted.

15.4 Creation/Changes to Statistical Analysis Plan

The person in charge of statistical analysis should create the Statistical Analysis Plan describing the statistical analysis plan and method for this clinical trial.

When the statistical analysis plan is to be changed, the sponsor will examine the validity of the change and impact on the evaluation in this clinical trial to decide whether or not the change should be made. When the statistical analysis plan should be changed, a revision history should be created describing the changes

- 105 -

16 ELECTRONIC CASE REPORT FORM

16.1 Procedure for Electronic Case Report Form Creation and Precautions

- (1) The investigators should create eCRFs using electronic data capture (EDC) system.
- (2) The investigators should create an eCRF per subject.
- (3) The appropriately trained investigator, subinvestigator, and/or study staff should enter the data that were collected in accordance with the protocol in the eCRFs. The eCRFs may be completed by, in addition to the investigator, those appointed in "List of subinvestigators/study staff."
- (4) The sponsor will provide an explanation of entry and correction, in the eCRFs in accordance with "Guide for input into case report forms (eCRFs)", to the investigator, subinvestigator, and/or study staff.
- (5) The investigators should create an eCRF per subject after the end of observation as soon as possible (as a general rule within 10 working days), and submit it to the sponsor.
- (6) The investigator should check the accuracy and validity of the data, and place name and a seal or sign the CRFs to be submitted to the sponsor.
- (7) The sponsor will retain the original CRFs submitted by the investigator. The study site or investigator should retain a copy of the submitted CRFs.

16.2 Changes or Corrections to Electronic Case Report Forms

- (1) For changes/corrections before placing the name and seal or signature, the relevant sites should be changed or corrected. However, for changes/corrections to an important content (considerations concerning informed consent, changes to abnormal variations, name of AEs and causality), reasons for changes/corrections should be described in the applicable field.
- (2) For changes/corrections after placing the name and seal or signature, in addition to (1), place the name and a seal or sign again after the changes/corrections.

